8.9. SAFETY ANALYSES

Safety will be assessed by vital signs, hematology and chemistry laboratory evaluations, ECGs, and AEs, including all TEAEs, treatment-related AEs, SAEs, and AEs leading to dose modification.

The primary safety endpoint is the incidence of TEAEs. The secondary safety endpoints include extent of exposure (PK), changes in laboratory parameters, and changes in ECGs.

AEs will be reported according to the NCI CTCAE version 5.0 or higher and coded according to the latest MedDRA version available at the time of database creation. The number and percent of subjects with any AE will be presented by System Organ Class and Preferred Term for each cohort and will be summarized by cohort. Vital signs, laboratory parameters, and ECG intervals will be summarized and listed by timepoint by study part.

AEs will be categorized according to MedDRA System Organ Class and Preferred Term. Additional subcategories will be based on event intensity (severity graded according to NCI CTCAE version 5.0) and relationship to study drug.

Deaths, SAEs, AEs of clinical interest, and AEs leading to study drug discontinuation will be tabulated on a per subject basis, as warranted by the data. These endpoints will be listed.

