1.4. BENEFIT/RISK ASSESSMENT

AdvSM is a serious and life-threatening disease that involves the rapid and abnormal proliferation of a clonal mast cell population. Depending on the subtype of AdvSM, the average life-expectancy of a patient can range from 2 to 41 months ([NCCN Systemic Mastocytosis, Version 2.2019](#); [Rossignol et al, 2019](#)). The pathogenesis of AdvSM is driven by activation of the KIT receptor, specifically through a mutation in exon 17 (D816V). There are approved therapies targeting *KIT* mutations in some regions for the treatment of patients with AdvSM; however, significant safety and tolerability issues have limited their use.

Bezuclastinib is a TKI that selectively targets *KIT* mutations, including D816V, as reported in nonclinical studies. Preliminary clinical activity with bezuclastinib has been observed in clinical Study PLX121-01 in subjects with solid tumors including GIST. A reduction in KIT exon 17 mutational burden was observed in subjects treated with bezuclastinib in that study, and this reduction was temporally associated with a reduction in tumor burden. Based on available clinical PK and nonclinical pharmacology data, it is expected that all dose levels to be studied may generate trough concentrations greater than IC₅₀ for *KIT* D816V, and therefore have the potential to be clinically active.

Upon initiation of this clinical study, a total of 78 healthy volunteers and subjects with solid tumors have received bezuclastinib as a single agent or in combination with pexidartinib or sunitinib across 2 clinical studies. Safety data indicate that bezuclastinib has acceptable safety and tolerability at total daily doses up to 1000 mg as a single agent or in combination with sunitinib. The important potential risks associated with bezuclastinib, which include hepatotoxicity (ie, asymptomatic elevations in liver enzymes), hematological toxicity (ie, anemia, thrombocytopenia, and neutropenia) and gastrointestinal toxicity (ie, nausea, vomiting, and diarrhea), were selected based on bezuclastinib nonclinical safety data, clinical experience, and the assessment of risks for products with similar mechanisms. AEs observed with bezuclastinib in the completed clinical studies were primarily low-grade, non-serious, reversible, and manageable via recommended dose modifications.

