2. TRIAL OBJECTIVES AND ENDPOINTS

Objectives and Endpoints:		
	Objectives	Endpoints
Part 1: Dose Optimization		
Primary	To identify a clinically active and tolerable systemic exposure range of bezuclastinib in subjects with AdvSM	
 Safety assessments (incidence of adverse events [AEs], serious adverse events [SAEs], changes from baseline in laboratory results) and dose modifications Pharmacokinetics (PK) and pharmacodynamic assessments Overall response rate (ORR) based on the modified IWG-MRT-ECNM response criteria per Central Response Review Committee (CRRC)
Part 2 Stage 1: Dose Confirmation		
Primary	To confirm the optimal dose of bezuclastinib in subjects with AdvSM	
 Safety assessments (incidence of AEs, SAEs, changes from baseline in laboratory results) and dose modifications PK and pharmacodynamic assessments ORR based on the modified IWG-MRT-ECNM response criteria per Central Response Review Committee (CRRC)
Part 2 Stage 2: Expansion		
Primary	To determine the efficacy of bezuclastinib at the selected optimal dose in subjects with AdvSM who are evaluable based on the modified IWG-MRT-ECNM response criteria	ORR defined as the percentage of subjects classified as confirmed responders (complete response [CR], CR with incomplete hematologic recovery [CRh], partial response [PR], and clinical improvement [CI]) according to modified IWG-MRT-ECNM response criteria as assessed by CRRC
Part 1 and Part 2		
Secondary	To characterize the safety and tolerability of bezuclastinib in subjects with AdvSM	Incidence of AEs, SAEs, AEs leading to dose modifications, and changes from baseline in laboratory results
	To evaluate additional efficacy parameters with bezuclastinib in subjects with AdvSM	Duration of response (DOR), defined as the date of the first documented response (CR, CRh, PR, or CI) to date of first documented disease progression or loss of response, or death from any cause, whichever occurs first, based on modified IWG-MRT-ECNM response criteria
		Time to response (TTR), defined as the date of randomization/first dose of study drug to the date of the first documented response (CR, CRh, PR, or CI) based on modified IWG-MRT-ECNM response criteria
		Progression-free survival (PFS), defined as the date of randomization/first dose of study drug to the date

Objectives and Endpoints:		
	Objectives	Endpoints

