8.2. DETERMINATION OF SAMPLE SIZE

Approximately 28 subjects will be randomized 1:1:1:1 into 4 dose cohorts (Formulation A) in Part 1, including up to 4 subjects who are non-evaluable per modified IWG-MRT-ECNM response criteria based on lack of evaluable organ damage per modified IWG-MRT-ECNM criteria. It was determined that approximately 6 subjects evaluable per modified IWG-MRT-ECNM response criteria per group (24 total) would allow for ruling out an ORR of 60% or higher if a dose group had an ORR estimate of 16.7% or less (ie, if the ORR for a dose is 1/6, the upper bound of the 1-sided 90% confidence interval is 51.0% via a Clopper-Pearson exact confidence interval). Dose decisions will be based on an assessment of safety, biomarker, and clinical efficacy, and PK endpoints at each dose, with summary statistics and figures being used to illustrate dose-response.

Part 2 of the study will enroll approximately 75 subjects who are evaluable per modified IWG-MRT-ECNM criteria and up to an additional 15 subjects with AdvSM who are non-evaluable per modified IWG-MRT-ECNM response criteria at study entry.

For Part 2 Stage 1, approximately 20 subjects who are evaluable per modified IWG-MRT-ECNM will be randomized in a 1:1 ratio to receive bezuclastinib 150 mg QD or 300 mg QD (Formulation B). It was determined that approximately 10 subjects evaluable per modified IWG-MRT-ECNM response criteria per group would allow for ruling out an ORR of 60% or higher if a dose group had an ORR estimate of 30.0% or less (ie, if the ORR for a dose is 3/10, the upper bound of the 1-sided 90% confidence interval is 55.2% via a Clopper-Pearson exact confidence interval). The determination of the optimal dose will be based on totality of the data including assessment of safety, biomarker and clinical efficacy, and PK endpoints at each dose level.

For Part 2 Stage 2, approximately 55 subjects who are evaluable per modified IWG-MRT-ECNM response criteria will be enrolled. The null hypothesis is that ORR for subjects who received bezuclastinib treatment will be the same as the historical control (28%) (RYDAPT SmPC, 2021). Assuming the ORR for subjects who received bezuclastinib is 60%, 55 evaluable subjects will provide at least 90% power to reject the null hypothesis based on a Chi square test at one-sided alpha of 0.025.

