8.8. QUALITY OF LIFE ANALYSES

The PGIC and change and percent change from baseline in the patient-reported outcomes and quality of life scales PGIS, MC-QoL, and MAS ([Appendix I](#)) will be summarized by study part and stage (Part 1, Part 2 Stage 1, or Part 2 Stage 2) and dose cohort. These endpoints will be listed as well.

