8.10. PHARMACOKINETIC AND PHARMACODYNAMIC ANALYSES

PK samples will be taken at various timepoints before and after dosing with bezuclastinib. Standard PK parameters will be estimated using noncompartmental methods. Bezuclastinib plasma concentrations and PK parameters will be summarized by study part and/or stage, dose and visit.

A number of pharmacodynamic parameters will be measured. Blood and bone marrow will be obtained at various timepoints throughout the study to determine the effects of bezuclastinib on PK/pharmacodynamic relationships, including *KIT* D816V mutation allele burden and serum tryptase levels as a measure of pharmacodynamic activity as a single agent. Histopathologic response will be evaluated based on the percent of mast cell infiltration in the bone marrow. At each timepoint, each of these parameters will be summarized by study part and dose cohort. In addition, the parameters over time will be plotted for each subject. An analysis of pre-study versus on-study samples will be performed. If data are sufficient, graphical exploratory analysis of PK/pharmacodynamic relationships may be performed.

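### Section 8.9 groups laboratory, vital-sign and ECG summaries by study part without dose cohort, in conflict with the by-dose safety assessment on which the dose decision rests

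*Protocol*

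**What the plan says.** Section 8.9 of the Protocol, and the Safety Analysis paragraph of the synopsis, give one grouping for these data: "Vital signs, laboratory parameters, and ECG intervals will be summarized and listed by timepoint by study part". Neither place mentions dose.

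The surrounding text treats other outcomes differently:

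- **Adverse events.** The sentence just before it in Section 8.9 presents them by System Organ Class and "Preferred Term for each cohort and will be summarized by cohort".
- **Patient-reported outcomes.** Section 8.8 groups them by part and stage ("Part 1, Part 2 Stage 1, or Part 2 Stage 2) and dose cohort").
- **Pharmacodynamics.** Section 8.10: "At each timepoint, each of these parameters will be summarized by study part and dose cohort". The same section summarizes pharmacokinetics by part and/or stage, dose and visit.
- **Efficacy.** Section 8.7 uses study part/stage and dose cohort.

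On purpose, Section 2 lists among the primary endpoints of both Part 1 and Part 2 Stage 1 the incidence of adverse events and "changes from baseline in laboratory results) and dose modifications". Section 8.2 says of Stage 1: "The determination of the optimal dose will be based on totality of the data including assessment of safety, biomarker and clinical efficacy, and PK endpoints", and adds that this is done for each dose level. For Part 1 it says the same of each dose and adds that summary statistics and figures will illustrate dose-response. Section 1.4 names as important potential risks "hepatotoxicity (ie, asymptomatic elevations in liver enzymes), hematological toxicity (ie, anemia, thrombocytopenia, and neutropenia" and gastrointestinal toxicity.

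**The concern.** Part 1 randomizes to four dose cohorts and Part 2 Stage 1 to two, and both exist to inform the choice of dose. Laboratory change is a primary endpoint in each. If Section 8.9 is followed as worded, the planned laboratory, vital-sign and ECG tables combine the doses being compared. No reason is given for treating these data differently from every other outcome, so it reads like a drafting omission. It is nevertheless a stated grouping, not a detail left open.

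The liver and blood-count risks in Section 1.4 are seen mainly in laboratory data, and Section 7.1.3 makes QTc prolongation of Grade 3 or higher an adverse event of clinical interest. At stake is whether a modest dose gradient in enzymes, counts or QTc appears in a planned summary, or has to be found by reading listings.

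**Working it through.** **Inputs**

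- Part 1: four cohorts of approximately 7 subjects (Section 1.3.3), 28 in total (Section 8.2).
- Part 2 Stage 1: two arms of approximately 10 evaluable subjects (Section 8.2), 20 in total.
- Total daily dose in Part 1: 100, 200, 400 and 400 mg (Table 4), so two cohorts share 400 mg/day.
- Part 1, Stage 1 and Stage 2 are analyzed separately (Section 8.1).

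**The plan's own per-dose figures.** Section 8.2 justifies the group sizes dose by dose, using the upper limit of a one-sided 90% Clopper-Pearson interval, which is the 0.90 quantile of Beta(x+1, n−x).

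- 1/6: Beta(2, 5) gives 51.03% (stated 51.0%).
- 3/10: Beta(4, 7) gives 55.17% (stated 55.2%).

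Both reproduce. They are not in dispute; they show that the dose group is the unit for which these segments were sized.

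**Effect of pooling.** If dose d has n_d subjects and mean shift δ_d, the pooled mean shift is Σ n_d δ_d / Σ n_d. For a shift δ confined to the affected dose or doses:

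| Segment | Affected | Share of δ shown |
|---|---|---|
| Part 1 | one cohort | 7/28 = 25% |
| Part 1 | both 400 mg/day cohorts | 14/28 = 50% |
| Part 2 Stage 1 | one arm | 10/20 = 50% |

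**Illustration with assumed values (not from the Protocol)**

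- A 20 msec mean QTc rise in one Part 1 cohort appears as 20 × 7/28 = 5 msec. In both 400 mg/day cohorts it appears as 20 × 14/28 = 10 msec. In one Stage 1 arm it appears as 20 × 10/20 = 10 msec.
- Three of 7 subjects (43%) with a raised ALT in one Part 1 cohort and none elsewhere appear as 3/28 (11%). In Stage 1, 3/10 (30%) against 0/10 appears as 3/20 (15%).

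**Which data depend on these summaries.** Section 7.2.1 records a laboratory or ECG abnormality as an adverse event only if it needs medical or surgical intervention, leads to discontinuation, delay or interruption of therapy, or comes with clinical signs or symptoms. The criteria in Table 6 that could lead to an interruption include:

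- transaminases above 8×ULN, above 5×ULN for more than 2 weeks, or above 3×ULN only together with bilirubin, INR or symptom conditions;
- Grade 4 thrombocytopenia for at least 7 days, or Grade 3 or worse with bleeding;
- QTc above 500 msec, or a rise above 60 msec.

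An asymptomatic ALT of 4×ULN with normal bilirubin and INR, an uncomplicated Grade 3 platelet fall, or a 30 msec QTc rise to a value below 500 msec can therefore stay out of the by-cohort adverse-event tables. For such data Section 8.9 supplies the only explicitly named summary, and it carries no dose level.

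**The case against.** The strongest reply is that the Protocol read as a whole does look at safety by dose.

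- Section 8.2 promises Part 1 summary statistics and figures to illustrate dose-response, and safety is among the endpoints in that sentence.
- Treatment-emergent adverse events, which Section 8.9 calls the primary safety endpoint, are shown by cohort and subdivided by severity grade.
- A laboratory or ECG abnormality that leads to a dose interruption becomes an adverse event, and so reaches those tables.
- Grade 3 or higher QTc, hepatic and bleeding events are reported on serious-adverse-event timelines (Sections 7.1.3 and 7.2.5) and tabulated (Section 8.9).
- The treatment-discontinuation trigger in Section 4.4 operates per dose cohort.
- Individual values are listed, and the steering committee and sponsor review all available data before the dose is chosen.
- Section 8.9 never says that doses will be averaged, and a statistical analysis plan may add dose-level tables.

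Much of this stands, and it confines the point to abnormalities below the adverse-event threshold. It does not remove the conflict. The Section 8.2 clause does not name laboratory or ECG data, whereas Section 8.9 does name them and fixes another grouping. Listings are not summaries. A by-dose analysis plan would have to go beyond the Protocol's stated wording.

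Three stronger inferences are not supported:

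- A reader might conclude that these data could not reveal a dose-toxicity relation at all. The listings, the by-cohort adverse-event tables and Section 8.2 show otherwise.
- A reader might take summaries by timepoint to leave out values from unscheduled visits. Section 8.9 does not say so, and the notes to Table 1 have unscheduled assessments recorded in the eCRF.
- A reader might take study part literally and pool both stages of Part 2, which would dilute a signal further. Section 8.1 keeps the stages apart.

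**Conclusion.** The point holds as an internal conflict with a limited consequence. Section 8.9 and the synopsis state a grouping without dose for laboratory, vital-sign and ECG data, against Section 8.2, the by-dose grouping of all the other outcomes and, for laboratory change, the primary endpoint in Section 2. Followed as worded, shifts below the adverse-event recording threshold have no explicitly planned summary by dose.

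The one-quarter figure is the case of a single affected Part 1 cohort; a harm driven by total daily dose could affect both 400 mg/day cohorts, and then half is shown. All shares assume equal cohorts at the planned sizes, complete data at the timepoint, and no shift at the other doses. Where the shift is graded across doses, the pooled mean is simply the average of the cohort shifts and the gradient is not displayed. Sample size, alpha and the Stage 2 efficacy test are unaffected. The correction is worth making before the tables are specified because it concerns a primary endpoint of both dose-comparison segments.

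**What to change.** In Section 8.9 and in the synopsis Safety Analysis paragraph, change the grouping of vital signs, laboratory parameters and ECG intervals to *by study part/stage, dose cohort and timepoint*. This brings them into line with Sections 8.8 and 8.10 and with the dose decision described in Section 8.2.

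The cost is one phrase in two places and some additional tables, with no new data collection. The small downside is that each summary will rest on about 7 subjects in Part 1 or 10 in Stage 1 and will be imprecise, so the tables should be read descriptively. Worst post-baseline grade shifts by dose cohort for liver tests and blood counts would be a useful optional addition in the statistical analysis plan, but the correction does not depend on them.

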8.10. PHARMACOKINETIC AND PHARMACODYNAMIC ANALYSES

PK samples will be taken at various timepoints before and after dosing with bezuclastinib. Standard PK parameters will be estimated using noncompartmental methods. Bezuclastinib plasma concentrations and PK parameters will be summarized by study part and/or stage, dose and visit.

A number of pharmacodynamic parameters will be measured. Blood and bone marrow will be obtained at various timepoints throughout the study to determine the effects of bezuclastinib on PK/pharmacodynamic relationships, including *KIT* D816V mutation allele burden and serum tryptase levels as a measure of pharmacodynamic activity as a single agent. Histopathologic response will be evaluated based on the percent of mast cell infiltration in the bone marrow. At each timepoint, each of these parameters will be summarized by study part and dose cohort. In addition, the parameters over time will be plotted for each subject. An analysis of pre-study versus on-study samples will be performed. If data are sufficient, graphical exploratory analysis of PK/pharmacodynamic relationships may be performed.

8.11. EXPLORATORY ANALYSES

Exploratory analyses will include pharmacodynamic markers (including *KIT* D816V mutation allele burden) and their relationship with clinical safety, efficacy, and PK, and an exploration of the changes in C-findings. The proportion of subjects with resolution of C-findings (including resolution of hypoalbuminemia and changes in the size of lytic lesions) will be assessed. Change in the number or pigmentation of cutaneous lesions will be assessed by photographs taken per standard of care.

9. STUDY ADMINISTRATION

9.1. GOOD CLINICAL PRACTICE STATEMENT

This study is to be performed in accordance with the protocol, the Declaration of Helsinki, the International Council on Harmonisation (ICH) Harmonised Tripartite Guideline for Good Clinical Practice (GCP), and all applicable local regulatory requirements.

9.2. INFORMED CONSENT

The Sponsor or its designee will provide a sample patient ICF for modification, as appropriate, by the Investigator. The ICF must include all elements required by ICH and GCP and must adhere to the IRB/IEC requirements and the ethical principles that have their origin in the Declaration of Helsinki.

The Investigator(s) at each center will ensure that the subject is given full and adequate oral and written information about the nature, purpose, possible risk, and benefit of the study. Subjects must also be notified that they are free to discontinue from the study at any time. The subject should be given the opportunity to ask questions and allowed time to consider the information provided.

The subject's signature (and date of signature) must be obtained on the ICF before any study-specific assessments or procedures are conducted.

The Investigator(s) must maintain the original, signed and dated ICF. A copy of the signed and dated ICF must be given to the subject.

The ICF and any other written information provided to the subjects will be revised whenever important new information becomes available that may be relevant to the patient's consent, or if there is an amendment to the protocol that necessitates a change to the content of the patient's informed consent. The Investigator will inform the subjects of changes in a timely manner and will ask the subjects to confirm continuation of their participation in the study by their signature on the revised ICF (if applicable). Any written ICF and written information must receive the approval/favorable opinion of the IRB/IEC in advance of use. Any additional approvals from the initial ICF should be forwarded to the Sponsor.

9.3. PATIENT CONFIDENTIALITY

The written ICF will explain that study data will be stored in a database, maintaining confidentiality in accordance with national data legislation. All data processed by the Sponsor or its representative(s) will be identified by subject number and study code.

The written ICF will also explain that for data verification purposes, authorized representatives of the Sponsor, a regulatory authority, and an IRB/IEC may require direct access to parts of the hospital or clinic records relevant to the study that include the patient's medical history.

The Investigator must ensure that the subjects' anonymity is maintained. On the eCRFs or other documents submitted to the Sponsor, subjects should not be identified by their names, but by

their assigned subject number and study code. Documents not for submission to the Sponsor, such as signed ICF, should be maintained in strict confidence by the Investigator.

9.4. INSTITUTIONAL REVIEW BOARD/INDEPENDENT ETHICS COMMITTEE REQUIREMENTS

The final study protocol, including the final version of the ICF, must be approved or given a favorable opinion in writing by an IRB/IEC at each clinical trial site. The Principal Investigator (PI) must submit written approval to the Sponsor before he or she can enroll any patient into the study.

The PI is responsible for informing the IRB/IEC of any amendment to the protocol. In addition, the IRB/IEC must approve all advertising used to recruit subjects for the study. The protocol must be reapproved by the IRB/IEC annually or as applicable.

Progress reports and notifications of SAEs will be provided to the IRB/IEC according to regulations and guidelines.

